7.9.3 Subject Disposition

The number of subjects included in each analysis population (randomized, ITT, safety and PP) will be summarized by treatment group, by treatment group within analysis center and by treatment group within investigational site. The number of subjects completed and discontinued (including the primary reason for discontinuation) will be summarized for each treatment group.

Subjects who are excluded from an analysis population will be summarized by the reasons for exclusion. Reasons subjects were not randomized will be summarized for subjects who did not enroll in the study.

7.9.4 Protocol Deviations

Protocol deviations will not be entered into the database. Only deviations leading to exclusion from analysis populations will be identified and summarized.

7.9.5 Demographic and Baseline Characteristics

All baseline summaries will be performed on the ITT, PP and safety populations.

Sex, race, ethnicity and Fitzpatrick skin type will be summarized by counts and percentages. Age will be summarized with descriptive statistics. Summaries of dichotomized age (less than median and greater than or equal to median) and categorized age (less than 18, 18 to less than median and greater than or equal to median) will also be included.

Subjects' baseline characteristics related to efficacy analyses will be summarized and compared between treatment groups to evaluate baseline balance between the treatment arms. Baseline inflammatory lesion count and baseline non-inflammatory lesion count will be compared using a two-way analysis of variance with factors of treatment group and analysis center. Baseline IGA will be compared using a Cochran-Mantel-Haenszel test of row means scores, stratified by analysis center.

Acne vulgaris history, including number of years since onset, anatomical areas affected and prior acne treatments, will be summarized by counts and percentages. If only the year is known for start of acne vulgaris the number of years since onset will be calculated by using January for

month and "01" as day. If only the year and month are known for start of acne vulgaris then onset will be calculated by using "01" as day.

Medical histories will be coded using the MedDRA dictionary and presented in a by-subject listing.

7.9.6 Prior and Concomitant Medications

Prior and concomitant medications will be coded to preferred name and anatomical therapeutic chemical (ATC) classification of ingredients using the WHO-DDE.

Counts and percentages will be provided to summarize the use of prior and concomitant medications other than the study drug reported throughout the study. The number and percent of subjects reporting medications will be summarized by ATC level 2 term and preferred name. Medications which start prior to first dose will be considered prior medications. Ongoing medications and medications ending after the date of first dose will be considered concomitant medications. Medications which are both prior and concomitant will be included in both summaries. Incomplete start and end dates which could be prior to first dose or after first dose will be considered prior to first dose.

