5.3.2 Exclusion Criteria

Subjects meeting any of the following criteria are not eligible for study participation:

1. Previous active treatment in Olumacostat Glasaretil (DRM01B) Gel trials

- 2. Females who are currently pregnant, lactating or planning to become pregnant during the course of the study
- 3. Known hypersensitivity to Olumacostat Glasaretil or its excipients
- 4. Any skin condition which may interfere with the evaluation of safety or, of acne vulgaris (e.g., rosacea; seborrheic dermatitis; perioral dermatitis; corticosteroid-induced acne or folliculitis)
- 5. Excessive facial hair that would interfere with diagnosis or assessment of acne vulgaris
- 6. Excessive sun exposure that could affect the clinical state of acne, in the opinion of the investigator or, anticipated use of tanning booths
- 7. Active cystic acne or acne congoblata, acne fulminans, and secondary acne
- 8. Two or more active nodulocystic lesions on the face
- 9. Screening clinical chemistry, hematology, or urinalysis laboratory value, deemed clinically significant, by the Investigator
- 10. Abnormal findings on screening ECG, deemed clinically significant by the Investigator
- 11. Subjects who are actively participating in an experimental therapy study or who have received experimental therapy within 30 days or 5 half-lives (whichever is longer) of the Baseline visit
- 12. Subjects who are a poor medical risk because of other systemic diseases or active uncontrolled infections, in the opinion of the investigator
- 13. Any other condition which, in the judgment of the investigator, would put the subject at unacceptable risk for participation in the study
- 14. Treatment with over-the-counter topical medications for the treatment of acne vulgaris including benzoyl peroxide, topical anti-inflammatory medications, corticosteroids, α-hydroxy/glycolic acid on the face within 2 weeks prior to Baseline
- 15. Treatment with systemic corticosteroids (use of intranasal and inhaled corticosteroids allowed for seasonal allergies and asthma) within 4 weeks prior to Baseline
- 16. Treatment with systemic antibiotics or systemic anti-acne drugs within 4 weeks prior to Baseline
- 17. Prescription topical retinoid use on the face within 4 weeks prior to Baseline (e.g., tretinoin, tazarotene, adapalene)

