6.5 Study Drug Application

Subjects will be instructed on the application of the study medication. The first dose of the study drug will be applied in the clinic for instructional purposes. Subjects are to apply the study drug twice daily (morning and evening) to a clean dry face.

Study drug is to be applied topically, to the entire face (forehead, nose, cheeks, and chin) by squeezing approximately ½ inch or slightly more than1centimeter long line of gel, onto a finger and spreading the gel over the face, avoiding the skin around the eyes, eyelids and mouth, until the face is completely covered. Study drug may be applied to all affected areas on the trunk (i.e., chest, shoulders and back) by spreading a thin layer of gel over the entire affected area.

Subjects are to be instructed to wash their hands prior to and immediately following study drug application.

Subjects should avoid washing the face or swimming within 2 hours after applying study medication.

Missed doses should be applied, provided there is at least an 8 hour window until the next scheduled dose.

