6.7 Study Drug Accountability

The Investigator or designee will be responsible for study drug accountability and records at the site. Study drug accountability records will document the receipt, dispensing and return of study drug and provide a complete account of all used and unused drug product. Study drug accountability records will be reviewed regularly throughout the study by the Sponsor/designee. Study medication will be returned to the Sponsor, or designee, at the end of the study, following final study drug accountability.

7 CONCOMITANT MEDICATIONS AND PROCEDURES

All medications (including over-the-counter drugs, vitamins, antacids and skin care products) taken during screening and throughout the study will be recorded on the eCRF. In addition, to ensure that the subject meets the acne treatment and medication exclusion criteria, all acne treatment and medications, including, any past isotretinoin, facial procedures, Vitamin A and hormonal therapy use will be recorded on the eCRF.

Medication entries should be specific to the generic name (if a combination drug, then marketed product name) and will include the dose, unit, frequency, route of administration, start date, discontinuation date, and indication. When listing medications indicated for acne, the area treated will be collected.

The Investigator should examine the acceptability of all concomitant procedures, medications, topical preparations and dietary supplements not explicitly prohibited in this study. In order to ensure that appropriate concomitant therapy is administered, subjects will be instructed to consult with the Investigator prior to taking any medication (either self-administered non-prescription drugs or prescription therapy prescribed by another physician).

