7.8.4 Per-Protocol (PP) Population

All subjects in the safety population who complete the Week 12 evaluation without any significant protocol violations will be included in the PP population and analyzed according to the treatment group they were randomized. The PP population will include subjects in the safety population who do not meet any of the following criteria:

- Violated the inclusion/exclusion criteria;
- Have taken any interfering concomitant medication;
- Did not attend the Week 12 visit:
- Have missed both the Week 4 and Week 8 study visits;
- Have not been compliant with the dosing regimen (i.e. subjects must apply 80-120% of the expected applications of study medication during participation in the study);
- Out of visit window at the Week 12 visit by ± 5 days.

Subjects that discontinue treatment or from the study due to an AE related to study treatment or documented lack of treatment effect will be included in the PP population. Prior to breaking the

blind, other additional criteria may be added to the list to accommodate for unforeseen events that occurred during the conduct of the trial that result in noteworthy study protocol violations.

All efficacy analyses will be performed on the PP population.

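### SAP 7.9.6 counts a medication as prior only when its partial end date straddles first dose, and its cut-offs leave out Day 1, so the concomitant-medication summaries can only under-count

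*SAP*

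**What the plan says.** SAP 7.9.6 sets two classes by date:

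- Prior: "Medications which start prior to first dose will be considered prior medications".
- Concomitant: "Ongoing medications and medications ending after the date of first dose will be considered concomitant medications".

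Overlap is allowed: "Medications which are both prior and concomitant will be included in both summaries". Nothing is said about a medication that meets neither definition. Partial dates get one rule for both ends of the interval: "Incomplete start and end dates which could be prior to first dose or after first dose will be considered prior to first dose".

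The timing fields that Protocol section 7 lists for each medication are "start date, discontinuation date, and indication" with the indication; no clock time is listed. Protocol 6.5 makes Day 1 an on-treatment day: "The first dose of the study drug will be applied in the clinic for instructional purposes". For adverse events, SAP 7.9.8.2 draws its line differently and counts onset on the date of first application as treatment-emergent.

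SAP 7.8.4 removes from PP subjects who "Have taken any interfering concomitant medication" and, as a separate criterion, subjects who breached the inclusion or exclusion criteria. SAP 7.1 mentions washout medications as something to be coded, but 7.9.6 gives no rule for them.

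**The concern.** A single rule for start and end dates works in opposite ways. Moving a doubtful start date back before first dose costs nothing, because concomitant status depends on the end date or the ongoing flag. Moving a doubtful end date back takes the medication out of the concomitant summary. The usual cautious choice is to assume on-treatment use where it cannot be ruled out; here every doubtful case is settled the other way.

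The Day 1 cut-off adds to this. A drug given only on Day 1 for an adverse event that began on Day 1 would not appear as concomitant, although the event itself would be counted.

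At stake is how complete the by-arm description of other treatment during the study will be. SAP 7.9.4 says that deviations are not entered in the database and that only those leading to exclusion from a population are identified, so the medication records carry much of the evidence on use of other acne products.

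**Working it through.** **1. Literal classification.** The plan gives no figure to reproduce, so the rules are applied to cases with Day 1 set arbitrarily at 15 March 2017. Prior means start before Day 1. Concomitant means ongoing, or end after Day 1. A straddling partial date counts as before Day 1.

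| Start | End | Under 7.9.6 | Under the fix |
|---|---|---|---|
| 23 Feb | 10 Mar | prior only | unchanged |
| 23 Feb | Mar, day missing | prior only | prior and concomitant |
| 23 Feb | 2017 only | prior only | prior and concomitant |
| Mar, day missing | Mar, day missing | prior only | prior and concomitant |
| 23 Feb | 15 Mar (Day 1) | prior only | prior and concomitant |
| 15 Mar | 15 Mar | neither | concomitant |
| 15 Mar | 16 Mar | concomitant | unchanged |
| Mar, day missing | 25 Mar | prior and concomitant | unchanged |
| 23 Feb | Apr, day missing | prior and concomitant | unchanged |
| 23 Feb | ongoing | prior and concomitant | unchanged |

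If each date is judged alone, a medication started on 18 March with end recorded as March also falls in neither class. A sensible programmer would avoid this, since a drug started after first dose cannot have ended before it.

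**2. Size, as an illustration only.** Assume a 30-day month, a month-only end date in the first-dose month, and a stop day uniform over the month. With Day 1 on day d, the share truly ending after Day 1 is (30 − d)/30:

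- d = 1: 29/30 = 97%
- d = 15: 15/30 = 50%
- d = 30: 0%

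With d also uniform there are 30 × 30 = 900 equally likely pairs:

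- end after first dose: 435/900 = 48.3%
- end on the same day: 30/900 = 3.3%
- end before first dose: 435/900 = 48.3%

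The current rule therefore misplaces 48.3% of such records by the SAP's own cut-off, or 465/900 = 51.7% if Day 1 counts as on treatment. The fix misplaces the 48.3% that ended earlier.

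**3. Would a washout breach be missed in PP?** The exclusion criteria in Protocol 5.3.2 count back from Baseline, for example "Prescription topical retinoid use on the face within 4 weeks prior to Baseline". The window is 2 weeks for over-the-counter topical products and androgen receptor blockers, and 4 weeks for systemic antibiotics, systemic anti-acne drugs and facial topical retinoids. With a month-only stop date in the first-dose month and Day 1 on day d, the longest possible gap is d − 1 days.

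- First dose 10 March, stop March: the gap is at most 9 days, so every possible date breaches both the 14-day and the 28-day window.
- 4-week products: every date breaches while d − 1 ≤ 28, that is up to day 29.
- 2-week products: every date breaches while d − 1 ≤ 14, that is up to day 15. Later in the month a compliant stop is possible, and the partial date leaves the question open.

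For month-only dates, most such cases therefore meet the separate PP criterion on eligibility violations whether the drug is labelled prior or concomitant.

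**The case against.** The strongest reply is that the section produces only descriptive counts. It enters no ITT model, and the stepwise secondary tests are confined to ITT. That stands.

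Three stronger readings are tempting, and the documents do not support them.

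- *A reader might infer that PP loses its protection against other acne drugs.* SAP 7.8.4 does not tie the interfering-medication criterion to the 7.9.6 classes, and step 3 shows that the eligibility criterion already catches most washout breaches. The on-study prohibitions (Protocol 7.2) and the early-termination rules (Protocol 10.2) also protect.
- *A reader might infer that about half of the partial dates in this trial will be misclassified.* The 48% follows from assumed uniform and independent days. It ignores that eligible subjects must have stopped washout products weeks earlier. The number of such records is unknown and could be zero.
- *A reader might infer that washout products are the likeliest to have partial stop dates.* Nothing in the documents says so. Washout duration is set at Screening, the discontinuation date is a listed field, and medications are asked about at Baseline and at every later contact.

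It is also fair to say that the fix swaps one error for another of similar frequency, and that a drug started before Day 1 is not lost, since it still appears in the prior summary. Both stand. What survives is the direction of the error, which 7.9.6 fixes one way, and the Day 1 gap. That gap cannot be closed by clock time because only dates are listed.

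**Conclusion.** The point holds as a wording fault with a one-directional effect. Under SAP 7.9.6, on-treatment use can be missed in the concomitant summary but not over-counted, and a medication confined to Day 1 appears in neither summary. No other section reverses this, and the adverse-event rule in the same SAP includes Day 1.

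The consequence is limited to the descriptive medication summaries, with an effect on PP only if the blinded review adopts this classification. The size in this trial cannot be computed. The 48% figure rests wholly on the uniform 30-day assumption and ranges from 0% to 97% with the calendar day of first dose. The change is worth making because it is cheap, not because any efficacy conclusion depends on it.

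**What to change.** In SAP 7.9.6, replace the concomitant definition and the partial-date sentence with:

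> An incomplete start date that could be before first dose is treated as before first dose. A medication is concomitant if it is ongoing or ends on or after the date of first dose; an incomplete end date that could be on or after first dose is treated as on or after first dose.

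In SAP 7.8.4, state whether the interfering-medication criterion uses this classification. Add that a doubtful date does not by itself exclude a subject from PP and is judged case by case in the blinded review.

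The cost is a few sentences and a small program change before unblinding. The downside is over-counting: under the uniform assumption about 48% of straddling month-only records would be shown as concomitant although they ended before first dose. For a description of on-treatment use that is the more cautious error. A footnote giving the number of medications classed on a partial end date would let the reader judge its weight.

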7.9.7 Efficacy Analyses

All efficacy analyses will be presented by treatment group for both ITT and PP populations.

7.9.7.1 Primary Efficacy Analyses

Absolute change from Baseline to Week 12 in inflammatory and non-inflammatory lesion counts will be analyzed using either parametric or non-parametric methods consistent with the statistical assumptions required to support the analyses. Specifically, the tests of superiority will be based on an ANCOVA with factors of treatment group and analysis center and the respective baseline lesion count as a covariate or on ranked data submitted to an ANCOVA with factors of treatment group and analysis center and the respective baseline lesion count as a covariate. If the treatment group by analysis center interaction effect is significant at an alpha less than 0.10, then the effect will be included in the model; otherwise it will be omitted.

A skewness test, based on the methods presented by J.H. Zar (1984) [1], will be applied to the residuals resulting from an ANCOVA. A two-sided p-value for the skewness test significant at 0.01 will imply the use of the non-parametric method. If a parametric analysis is indicated, the results of the parametric analysis will be considered the primary analysis. Should a non-parametric analysis be indicated, the absolute or percent changes in inflammatory and non-inflammatory lesions will be rank-transformed prior to submitting them to the ANCOVA. Results of the rank-transformed analyses then will be considered the primary analysis; however, results of the non-ranked transformed analyses will also be presented. That is, the primary

analyses for inflammatory and non-inflammatory lesion counts will be determined by the treatment group by analysis center interaction p-value and the skewness p-value as described in the table below:

Interaction P-Value	Skewness P-Value	Analysis Model
< 0.10	< 0.01	Ranked ANCOVA with factors of treatment, analysis center and treatment by analysis center interaction and the respective baseline lesion count as a covariate
≥ 0.10	< 0.01	Ranked ANCOVA with factors of treatment and analysis center and the respective baseline lesion count as a covariate
< 0.10	≥ 0.01	ANCOVA with factors of treatment, analysis center and treatment by analysis center interaction and the respective baseline lesion count as a covariate
≥ 0.10	≥ 0.01	ANCOVA with factors of treatment and analysis center and the respective baseline lesion count as a covariate

Note that interaction and skewness p-values will be computed for each imputation of multiply-imputed data. Model determination will depend on averaged p-values, computed by finding the mean p-values across all imputations.

The proportion of subjects who are dichotomized to success at Week 12 will be analyzed using a logistic regression with factors of treatment group and analysis center.

The sensitivity analysis for absolute change in lesion count will include a skewness test, based on the methods presented by J.H. Zar (1984) [1]. A ranked repeated measures analysis of covariance with factors of treatment group, visit, analysis center and treatment by visit interaction, and the respective baseline lesion count as covariate will also be included. Values will be ranked across all visits (i.e. visit will be ingored when ranking) and the baseline covariate will not be ranked.

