11.3 Primary Efficacy

Absolute change from baseline to Week 12 in inflammatory and non-inflammatory lesion counts will be analyzed using either parametric or non-parametric methods consistent with the statistical assumptions required to support the analyses. Specifically, the tests of superiority will be based on an ANCOVA with factors of treatment and analysis center and the respective Baseline lesion count as a covariate or on ranked data submitted to an ANCOVA with factors of treatment and analysis center and the respective Baseline lesion count as a covariate. If the treatment-by-

analysis center interaction effect is significant at an alpha less than 0.10, then the effect will be included in the model; otherwise it will be removed.

A skewness test, based on the methods presented by J.H. Zar (1984) [14], will be applied to the residuals resulting from an ANCOVA. A two-sided p-value for the skewness test significant at 0.01 will imply the use of the non-parametric method. If a parametric analysis is indicated, the results of the parametric analysis will be considered the primary analysis. Should a non-parametric analysis be indicated, the absolute or percent changes in inflammatory and non-inflammatory lesions will be rank transformed prior to submitting them to the ANCOVA. Results of the rank-transformed analyses then will be considered the primary analysis; however, results of the non-ranked transformed analyses will also be presented.

The proportion of subjects who are dichotomized to success at Week 12 will be analyzed using the logistic regression test stratified by analysis center.

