7. STATISTICAL METHODS AND ANALYSIS

7.1 General Methodology

All analyses will be performed using SAS® Version 9.3 or later. No interim analyses are planned. Except where noted, all statistical tests will be two-sided and will be performed at the 0.05 level of significance.

Descriptive statistics will be used to provide an overview of the efficacy and safety results. For categorical parameters, the number and percentage of subjects in each category will be presented. For continuous parameters, descriptive statistics will include n (number of observations), mean, SD, median, minimum and maximum. Appropriate inferential statistics will be used for the primary, secondary and exploratory efficacy variables.

The primary method of handling missing efficacy data will be the method of Markov Chain Monte Carlo (MCMC) multiple imputation.

The primary method of dichotomizing the IGA score will be to consider a subject a "success" if the IGA at a post-baseline visit is 0 or 1 and 2 or more grades lower than at Baseline; otherwise the subject will be considered a treatment "failure".

Reported AEs, medical history terms, prior and concomitant procedures and therapies and washout procedures will be classified on the basis of Medical Dictionary for Regulatory Activities (MedDRA) terminology, Version 19.1. Prior and concomitant medications and washout medications will be classified on the basis of World Health Organization Drug Dictionary (WHO-DDE) terminology, Format B2, Version March 1, 2016.

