7.3.1 MCMC Multiple Imputation

7.3.1.1 Lesion Count Variable Missing Data Imputation

A total of 4 random seeds will be needed to use PROC MCMC to impute inflammatory lesion counts and non-inflammatory lesion counts for the two treatment groups. Those 4 random seeds have been pre-specified by using a random number generator:

- Inflammatory Lesion Counts; Olumacostat Glasaretil Gel, 5.0%: Seed= 195361148;
- Inflammatory Lesion Counts; Olumacostat Glasaretil Gel, Vehicle: Seed= 2099102059;
- Non-Inflammatory Lesion Counts; Olumacostat Glasaretil Gel, 5.0%: Seed= 325230329;
- Non-Inflammatory Lesion Counts; Olumacostat Glasaretil, Vehicle: Seed= 936128187.

After imputing with PROC MCMC, the absolute change in lesion counts for Baseline minus the 12-week value will be computed. Each complete data set will be analyzed with an ANCOVA with factors of treatment group and analysis center and the respective baseline lesion count as a covariate. A factor of treatment group by analysis center will be added if necessary, and appropriate modifications will be made should the analysis be based on a non-parametric method. The results from these analyses will be combined using SAS PROC MIANALYZE.

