7.3.1.2 IGA Missing Data Imputation

A total of 2 random seeds will be needed to impute IGA for the two treatment groups. Those 2 random seeds have been pre-specified by using a random number generator:

- IGA; Olumacostat Glasaretil Gel, 5.0%: Seed= 322979853;
- IGA; Olumacostat Glasaretil Gel, Vehicle: Seed= 1313477781.

After imputing with PROC MCMC, the dichotomous success rate (clear or almost clear with at least a 2-point change from Baseline) will be computed. The 12-week estimated IGA values will be rounded to the nearest integer value prior to evaluating the success rate. Each complete data

set will be analyzed with a logistic regression with factors of treatment group and analysis center. The results from these analyses will be combined using SAS PROC MIANALYZE.

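### A 0.10 interaction pre-test chooses the primary lesion-count model, and the SAP does not say how centres are weighted once the interaction is in it

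*SAP*

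**What the plan says.** SAP 7.9.7.1 analyses absolute change in each lesion count by ANCOVA with treatment group, analysis center and the matching baseline count. If the treatment-by-centre "interaction effect is significant at an alpha less than 0.10, then the effect will be included in the model". A four-row table crosses this result with a skewness test, so two of its four rows contain the interaction. For imputed data the rule is: "Model determination will depend on averaged p-values, computed by finding the mean p-values across all imputations".

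The same gate appears in Protocol 11.3 ("then the effect will be included in the model; otherwise it will be removed") and in SAP 7.3.1.1 ("A factor of treatment group by analysis center will be added if necessary"). SAP 7.9.7.2 applies the same ANCOVA method to the percent-change secondaries, which are the first two steps of the ordered testing in SAP 7.6.

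The IGA co-primary is treated differently. In SAP 7.9.7.1 its success proportion "will be analyzed using a logistic regression with factors of treatment group and analysis center", with no rule for adding the interaction. SAP 7.5 separately tests the interaction for all three co-primaries as a consistency check.

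The SAP gives no sum-of-squares type and no LS-mean weighting for the treatment test. LSMean occurs only in its abbreviation list.

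**The concern.** In the additive model the treatment effect is an average of centre differences weighted by information. With the interaction in the model, a single treatment effect exists only after a centre weighting has been chosen. SAP 7.3 sends one estimate and its standard error per imputed data set to PROC MIANALYZE, but in two of the four table rows the text does not define that estimate. The common software default weights every centre equally, whatever its size.

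The quantity estimated, its variance and its test can therefore change on the outcome of a noisy preliminary test, for two of the three co-primaries and not the third. At stake are a treatment test that does not hold 5% in the trials where the term was selected, and some loss of power for non-inflammatory lesions. The sample-size section does not mention the pre-test. The gate itself is also not a 0.10-level test once p-values are averaged, because a mean of p-values is not a p-value.

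**Working it through.** **Plan's own figures (SAP 4.2), normal approximation.**
- Inflammatory, 300/150: SE = 11.00 × √(1/300 + 1/150) = 1.10; 5.51/1.10 = 5.01; power = Φ(5.01 − 1.96) = 99.9%, consistent with at least 95%.
- Non-inflammatory, 450/225: SE = 16.72 × √(1/450 + 1/225) = 1.365; 5.03/1.365 = 3.68; power = Φ(1.72) = 95.7–95.8%, against 95% stated.
- IGA, 20.5% v 9.6% with continuity correction: 222 vehicle and 444 active, reproduced exactly.
- Non-inflammatory at the planned 467/233: SE = 1.341; 5.03/1.341 = 3.75; power = 96.3%.

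**Two estimators.** For centre c with a active and v vehicle subjects, let w = av/(a + v), d the centre difference and K the number of centres.
- Additive: Σwd/Σw, variance σ²/Σw.
- Equal-weight: Σd/K, variance σ²Σ(1/w)/K².
- Variance ratio: Σw·Σ(1/w)/K², which is 1 only if all w are equal.

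**Why selection matters.** Under a homogeneous effect the covariance of the additive estimate with (d − additive estimate) is zero. The additive residual sum of squares is also independent of the interaction F. The additive test therefore stays at 5% whether or not the gate fires. For the equal-weight estimate the covariance is σ²[1/(Kw) − 1/Σw], which is non-zero when centre sizes differ. Selecting a large interaction thus selects extreme equal-weight estimates. It also selects small residual variances. The variance route alone gives 5.1–5.4%. With residual variance treated as known, the covariance route still gives 6.0% at a site-size coefficient of variation of 1.0.

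**Simulation inputs.** From the documents: about 50 sites, 700 subjects at 2:1, pooling within country to 10 active and 5 vehicle (SAP 7.5), difference 5.03, SD 16.72, gate at 0.10, test at 0.05 two-sided. Assumed: gamma-distributed site recruitment (shape 0.8 to 8), blocks of 3, country split 80/12/8%, handling of a lone leftover site, equal-weight contrast when the term is in. There were 1,000,000 trials per row. Missing data and the ranked option were not simulated. The documents give no number of centres; the ceiling is 700/15 = 46.

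| Mean centres | Error if term in | Error, additive, same trials | Power if term in | Power, additive, same trials | Overall error | Overall power |
|---|---|---|---|---|---|---|
| about 25 | 6.1% | 4.9% | 92.7% | 96.2% | 5.2% | 96.0% |
| about 29 | 5.8% | 5.1% | 94.1% | 96.4% | 5.1% | 96.1% |
| about 33 | 5.6% | 4.9% | 94.9% | 96.2% | 5.1% | 96.1% |
| about 35 | 5.5% | 5.1% | 95.8% | 96.3% | 5.1% | 96.2% |

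The term entered in 10.0% of trials in every row. The equal-weight SE was 1.7% (35 centres) to 9% (25 centres) larger. Inflammatory power stayed above 99.9%. Further simulations with other site-size assumptions widen the conditional error to 5.3–6.4%; conditional power stays within about 93–96%.

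**Overall effect by hand.** Worst-case error: 5 + 0.10 × (6.4 − 5) = 5.14%. Worst-case power loss: 0.10 × (96.3 − 92.7) = 0.36 points.

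**Averaged-p gate.** A small imputation run (300 trials per setting, 8–20% missing) gave entry rates of 6.7–8.0%. The Monte Carlo SE is √(0.07 × 0.93/300) = 1.5 points, so a rate below 10% is likely but not precisely measured. If the two endpoints were independent, at least one would receive the term in 1 − 0.90² = 19% of trials on complete data, or about 13–15% at 6.7–8.0%.

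**If centre effects truly vary.** With an assumed SD of 3 or 5 lesions and about 29 centres, the term enters in 26% or 58% of trials. Power when it is in is 92.9% or 90.6%, against 94.8% or 92.0% for the additive test in the same trials. Overall power is 94.35% v 94.82%, or 91.28% v 92.07%, a loss of 0.5 or 0.8 points.

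**The case against.** The rule is fully prespecified, so no analyst chooses between models after seeing the data. When an interaction appears, SAP 7.5 already requires a search for extreme centres and a re-analysis without them. Under genuine heterogeneity, equal weighting of centres is a defensible target. The average cost is a fraction of a point. All of this stands, and it limits the severity.

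It does not remove the point. Prespecifying the gate fixes which model applies, but not what the treatment estimate means once the interaction is in. The SAP 7.5 sensitivity analysis drops centres; it does not define the primary contrast. If equal weighting is the intended target, it should apply whatever the pre-test shows, and the plan should say so.

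Stronger readings are tempting. A reader might infer that the SAP prescribes an equal-weight average, or that it implies about 35 centres. It states neither: equal weighting is an assumption, and 35 is the near-even-recruitment end of a simulated range. A reader might also put the inflation down to an underestimated residual variance alone. With uneven centres, most of it comes from the correlation between the equal-weight estimate and the selected interaction.

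**Conclusion.** The point holds at low to moderate severity. The main defect is that the primary lesion-count estimate, and through SAP 7.9.7.2 the percent-change secondaries, can switch centre weighting on a random result, with the second weighting unstated. If that weighting is equal and there is no true heterogeneity, the trials where the term enters have type I error of about 5.3–6.4% and non-inflammatory power of about 93–96%, against about 96.3% for the additive model. Over all trials, error is 5.0–5.2% and the power loss is under about 0.4 points. Inflammatory power is not materially affected.

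A reader might infer that the trial's overall error rate is seriously inflated, or that a large power loss is likely. The documents support neither. The heterogeneity results rest on centre-effect SDs that no document gives, of a size approaching the whole 5.03-lesion effect. If centres are regarded as random, with real heterogeneity and a zero mean effect, both fixed-effect tests exceed 5% (about 7–11%), so the pre-test is not the cause of that. The figures depend on the assumed site-size spread and contrast; the ranked rows were not examined.

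**What to change.** Before unblinding:
- In SAP 7.9.7.1, SAP 7.3.1.1 and Protocol 11.3, make treatment group, analysis center and the respective baseline count the primary lesion-count model whatever the interaction p-value. The percent-change secondaries follow through SAP 7.9.7.2.
- Delete the interaction column of the model table, leaving the two skewness rows, and remove the averaged-p rule for the interaction.
- In SAP 7.5, report the interaction test, the interaction model and the centre-specific differences as supportive output, and state how centres are weighted in any overall estimate from that model.

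The cost is wording only: no new data, and every analysis is still run. With the additive model fixed, type I error is 5.0% and non-inflammatory power 96.3% at 467/233. The one thing given up is that the interaction model is no longer primary when heterogeneity appears.
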